3.2 Secondary Endpoints

The following secondary endpoints will be evaluated using descriptive statistics to provide further information related to the safety and performance of the Pristine™ Long-Term Hemodialysis Catheter. All secondary endpoints will be summarized with descriptive statistics.

- *Rate of freedom from catheter-related bloodstream infection (CRBSI)*, defined by 2019 KDOQI Guidelines for CRBSI through 1-month, 3-months, 6-months, and 12 months post-index procedure.

- *Rate of freedom from Device and/or Procedure-related adverse events*, at 1-month, 3-months, 6-months, and 12 months post-index procedure.
- *Rate of Technical Success*, defined as the successful placement of the Pristine™ Long-Term Hemodialysis Catheter, as assessed by the Investigator during the Index Procedure.
- *Overall Participant Survival Rate* at 1-month, 3-months, 6-months, and 12 months post-index procedure, defined as the proportion of participants that have not died from any catheter related complication.
- *Overall Catheter Survival Rate* at 1-month, 3-months, 6-months, and 12 months post-index procedure, defined as the proportion of Pristine™ Catheters that have not been removed for any cause.
- *Overall Patency Rate*, at 1-month, 3-month, 6-months, and 12-months post-index procedure, defined as the Pristine™ catheter having the ability to achieve a mean dialysis blood flow of $\geq 300\text{mL/min}$ without need for additional interventions.^{5,6}

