7.4 Participant Follow-Up

7.4.1 Follow-Up Intervals and Methods

Enrolled participants will have follow-up visits at 1-month, 3 months, 6-months, and 12-months via either in person visit or telephone call. For participants into whom the Pristine™ Catheter was introduced during the index procedure, but procedure success was not achieved, only the procedure eCRF will be collected and limited to the collection of safety events and interventions for up to 30 days.

Follow-up windows will be calculated from the index procedure date. Refer to Section 1.2 for an overview of follow-up window time frames and requirements for each visit. The

following data will be collected and documented on the appropriate eCRF for each follow-up unless otherwise specified for treated participants:

- Hemodialysis Catheter Assessment:
 - Document how the participant has been receiving hemodialysis and document the date of the participant's last HD session.
- Dialysis Session Blood Flow Rate:
 - If dialyzing through the Pristine™ Catheter, document the reported dialysis sessions and details such as date of dialysis session, average blood flow rate, number of line reversals, and length of dialysis session.
- If Needed:
 - Documentation of any protocol deviations that have occurred since the last follow-up.
 - Documentation of occurrence and / or status of AEs since the last follow up (refer to Section 9).
 - Any catheter reinterventions the participant has undergone since the prior follow-up.

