16 APPENDICES

Appendix A - Study Definitions

Appendix B - IFU

16.1 Appendix A - Definitions

Term	Definition
Access Censoring Events	Include participant transfer to Peripheral dialysis, kidney transplantation, AVF, AVG, or the event of a participants premature discontinuation in the investigation due to withdrawn consent, withdrawal by PI, LTF, or participant death (refer to abbreviations for definitions).
Active Participant	An investigation participant who has not completed all required investigation follow-up and who has not prematurely discontinued participation in this clinical investigation (refer to Section 6.5) at the timepoint of reference.
Adjunctive Procedure	Procedure(s) completed during the index procedure (prior to leaving the procedure room) as part of SOC procedures. Procedures to ensure HD continuity, as well as procedures to address AEs.
Adverse Device Effect (ADE)	An ADE is an AE that is considered to be related to the use of the Pristine™ Catheter. This includes AEs resulting from insufficient or inadequate IFU, operation, or any malfunction of the Pristine™ Catheter. Additionally, this definition includes any event resulting from use error or from intentional misuse of the Pristine™ Catheter.
Adverse event (AE)	
An AE is defined as any untoward medical occurrence, unintended disease or injury, or untoward clinical signs (including abnormal laboratory findings) in participants, users, or other persons, whether or not related to the Pristine™ Catheter and whether anticipated or unanticipated. For users or other persons, this definition is restricted to events related to the use of the Pristine™ Catheter.
 
Note: Pre-existing conditions should be considered as part of the participant's medical history and should not be reported as an AE unless there is a substantial increase in severity or frequency of the condition, which has not been attributed to natural history.
 
Exacerbation of an existing condition should be reported as an AE if the event meets the CIP definition of an AE.

All Interventions [Post Creation / After First Use]	The number of interventions [post creation / after first use] inclusive of all interventions (facilitation, maintenance, and HD continuity interventions).

Term	Definition

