### **Binary Analysis**

Subject will be considered as loss of overall patency if subject has experienced one of the following events:

- Subject undergoes re-intervention and re-intervention date is after the first dialysis session date
  - **Hemodialysis Catheter Re-Interventions CRF:** Date of Re-intervention > **Procedure Overview Details-Part 2 CRF:** Date of first dialysis session and subject will be considered as a failure at re-intervention date
- Subject has not been able to maintain the patency since last visit
  - **Most Recent Dialysis Session Blood Flow Rate CRF:** Was the catheter able to maintain patency since the last visit (Have the ability to achieve a mean dialysis blood flow of  $\geq 300\text{mL/min}$ )? No . The subject will be considered as a failure at Catheter Dysfunction Date

The subject will become a failure at the earlier occurrence of the above two events. If the subject has lost the overall patency prior to the upper limit of visit window subject will be counted as a failure for a given visit.

If the subject has not become failure and experience one of the following events prior to the lower limit of visit window, then subject will be considered as non-evaluable at the earliest occurrence of following event dates.

- Catheter has been removed due to Kidney Transplant, Transferred to AVG/AVF, Peritoneal Dialysis, Withdrawal of Care, or Other reasons  
*Hemodialysis Catheter Re-Interventions CRF page: Catheter removal Equals Yes AND Reason for catheter removal Equals: Kidney Transplant, Transferred to AVG/AVF, Peritoneal Dialysis, Withdrawal of Care, or Other*  
OR
- Subject has discontinued from the study.

If the subject has experienced any of the above **non-evaluable** events prior to the lower limit of visit window subject will be counted as a non-evaluable for a given visit; else subject will be considered as a success for a given visit.

The overall patency rate will be reported with 95% confidence interval from the exact binomial method. The analysis will be performed on the mITT population through 1-month, 3-months, 6-months, and 12-months.

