## **6.7 Most Recent Dialysis Session Blood Flow Rate**

Dialysis session blood flow rates reported in scheduled and unscheduled visits will be presented in a listing for mITT population.

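### SAP 5.3.6 scores a Pristine catheter as patent when it is in place but no longer used, or was not assessed at the visit

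*SAP*

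**What the plan says.** Protocol 3.2 defines Overall Patency as the catheter's ability to reach a mean dialysis blood flow of at least 300 mL/min "without need for additional interventions", at 1, 3, 6 and 12 months. The Binary Analysis in SAP 5.3.6 turns this into four outcomes:

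- **Failure by re-intervention:** "Subject undergoes re-intervention and re-intervention date is after the first dialysis session date".
- **Failure by site answer:** 'No' to "Was the catheter able to maintain patency since the last visit". The item states the 300 mL/min threshold, and a 'No' is dated by the catheter dysfunction date.
- **Non-evaluable:** the catheter was removed (transplant, AVG/AVF, peritoneal dialysis, withdrawal of care, other) or the participant discontinued before the lower window limit. In that case "subject will be counted as a non-evaluable for a given visit".
- **Everyone else:** "else subject will be considered as a success for a given visit". The KM Analysis treats the same people as event free and censors them on the visit day.

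Three other places bear on this. Protocol 7.4.1 has sites record at each follow-up how the participant is being dialysed and when the last session was. It asks for flow data conditionally: "If dialyzing through the Pristine™ Catheter, document the reported dialysis sessions and details such as date of dialysis session, average blood flow rate". SAP 6.7 states the use of those flows: "Dialysis session blood flow rates reported in scheduled and unscheduled visits will be presented in a listing for mITT population". Protocol Appendix A, under Access Censoring Events, says these "Include participant transfer to Peripheral dialysis, kidney transplantation, AVF, AVG" (the first presumably meaning peritoneal dialysis), along with premature discontinuation. It does not require catheter removal.

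**The concern.** Success is the residual category, so it needs no positive evidence. Two groups can reach it without anyone having observed a working catheter: participants who have moved to another access while Pristine stays in place, and participants still in the study whose patency item is blank or whose visit was missed.

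Both are foreseeable. The protocol background describes tunneled catheters as a bridge to, among other things, fistula maturation. Exclusion criterion 3 keeps out people already waiting for a fistula or graft to mature, so transfers will come from accesses created after enrollment and will tend to fall at the later visits. Protocol 7.5 keeps participants in follow-up until the catheter is removed, and Protocol 8.1.1 keeps those who miss a single visit.

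At stake is a descriptive rate, but Protocol section 3 says that study results are meant for the device labeling. A patency rate that includes unused or unassessed catheters would describe something other than the defined endpoint.

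**Working it through.** The documents give no expected patency rate, sample size or power for this endpoint, so there is no figure to reproduce. The check is a trace of the SAP 5.3.6 rule, then an illustration with assumed counts.

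**Trace**

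| Situation at a visit | Result under SAP 5.3.6 |
|---|---|
| Re-intervention after first dialysis | Failure |
| Site answers 'No' | Failure at dysfunction date |
| Removed for infection or dysfunction after first dialysis | Failure (entered on the Re-Interventions CRF) |
| Removed for transplant, AVG/AVF, peritoneal dialysis, withdrawal of care or other, before the window | Non-evaluable |
| Discontinued before the window | Non-evaluable |
| Dialysing by another access, Pristine in place, no prior failure, no 'No' | **Success** |
| Item blank or visit missed, still in study, no prior failure | **Success** |

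The last two rows are the problem. In the second to last, Protocol 7.4.1 requires no flow entry, the non-evaluable rule does not apply because the catheter has not been removed, and Appendix A would have censored at the transfer. In the Kaplan-Meier analysis the same person stays in the risk set to the visit day, although a catheter that is not used has little chance of being found to fail.

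**Direction.** Let n be the number evaluable under the SAP, s the number scored patent, and u the successes that should be non-evaluable. The rate moves from s/n to (s − u)/(n − u). The drop is

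s/n − (s − u)/(n − u) = u(n − s) / [n(n − u)],

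which is positive whenever there is at least one failure. For these participants the bias can only be upward, and it grows with the failure fraction.

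**Size (all s and u are assumptions).** n = 100 is a round number. n = 121 is 142 × 0.85 = 120.7, rounded, from the planned enrollment and the 15% attrition assumed through 90 days in SAP 2.4; later visits would have fewer.

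| n | s | u | As written | Corrected | Drop (points) |
|---|---|---|---|---|---|
| 100 | 70 | 10 | 70.0% | 60/90 = 66.7% | 3.3 |
| 121 | 109 | 6 | 90.1% | 103/115 = 89.6% | 0.5 |
| 121 | 109 | 12 | 90.1% | 97/109 = 89.0% | 1.1 |
| 121 | 97 | 6 | 80.2% | 91/115 = 79.1% | 1.0 |
| 121 | 97 | 12 | 80.2% | 85/109 = 78.0% | 2.2 |

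For scale, the exact 95% interval for 109/121 is 83.3% to 94.8%.

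**Discordant flows, a separate question.** If 3, 6 or 12 of the 109 successes had a recorded flow below 300 mL/min with 'Yes' ticked and were counted as failures, the rate would be 106/121 = 87.6%, 103/121 = 85.1% or 97/121 = 80.2%. This shows what a sensitivity analysis might reveal; it does not measure an error in the rule.

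**The case against.** The strongest reply is that the rule is sounder than it looks. Three stronger readings are tempting, and the documents do not support them.

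- *Patency is success unless a site ticks 'No'.* Re-intervention is an independent failure route, and there is a non-evaluable category.
- *Everyone no longer dialysing through Pristine counts as patent.* Participants whose catheter was removed, or who discontinued, before the window are failures or non-evaluable. Only catheters still in place but unused, and missing assessments, default to success.
- *Ignoring the recorded flows contradicts the endpoint definition.* Protocol 3.2 speaks of ability to achieve the flow, and the CRF item asks exactly that, with the threshold, over the whole interval since the last visit. A session can run below 300 mL/min for reasons unrelated to the catheter. Scoring on recent-session flows alone could also turn a mid-interval failure into a success and would lose the dysfunction date.

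Those replies stand. Three others stand in part. Access Censoring Events is a glossary term that no endpoint section invokes, and the glossary contains text from another device (the WavelinQ system appears under the U(S)ADE entry). The departure from Appendix A is therefore an inconsistency to resolve, not proof of a governing rule; the lack of evidence of function remains either way. SAP Appendix 2 (Derived Data Specification) is listed but not shown and might say how the item is handled when another access is in use. Finally, some features push the rate down: failures count to the upper window limit, and elective removals, if read literally as re-interventions, would be failures (with 6 or 12 such removals, 109/127 = 85.8% or 109/133 = 82.0%). The removals are a separate ambiguity about different participants, and neither feature reliably offsets the one described here.

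**Conclusion.** The point holds for two groups without a prior failure: participants dialysing by another access with Pristine in place, and participants in the study with no patency answer for the visit. SAP 5.3.6 scores both as patent, or event free to the visit day, without evidence of function. For transfers this departs from Protocol Appendix A.

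The bias from these groups is upward. Its size is unknown because the documents give no transfer or missed-visit rate. In the assumed cases it runs from 0.5 to 3.3 points, well inside the exact interval for a rate near 90%. The conclusion assumes that Appendix 2 does not already handle these cases.

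A reader might infer that the study's main result is at risk. It is not: Protocol 10.6 makes the secondary endpoints descriptive, and the primary Poisson test and the sample size do not use patency. The change is still worth making before analysis, because it is cheap and the rate may reach the labeling.

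**What to change.** Amend SAP 5.3.6, for participants without a prior failure:

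1. **Other access in use.** Once the Hemodialysis Catheter Assessment shows dialysis by another route, censor at the last session through Pristine (KM). In the binary analysis treat the participant as non-evaluable, using the same lower-window cut-off as for removals.
2. **No answer.** Treat a visit without a patency answer as non-evaluable unless a later visit's answer covers that interval. In the KM analysis, do not carry such a participant as event free past the last answered visit.
3. **Flow criterion.** Keep the Yes/No item and its dysfunction date as the main criterion. Add a sensitivity analysis that counts a recorded mean session flow below 300 mL/min with 'Yes' ticked as a failure, and report the number of discordant cases.

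The cost is SAP wording and programming, since route of dialysis, session dates and flows are already collected under Protocol 7.4.1. If the exact switch date is not captured, the last logged Pristine session can stand in. The price is fewer evaluable participants at 6 and 12 months and a slightly lower stated rate. The sensitivity analysis will also count some sessions that ran slowly for non-catheter reasons, which is why it should not replace the main criterion.

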### **KM Analysis**

KM analysis will be used to estimate the time from the date of index procedure to the date of overall patency loss and to determine the overall patency rate at 1-, 3-, 6-, and 12-months. The loss of overall patency is considered as the event.

Subjects that have not reached overall patency loss (event) will be censored or considered event free as described below.

- If the subject has experienced following events, subject will be censored at the earliest date of those events.

- Catheter has been removed due to Kidney Transplant, Transferred to AVG/AVF, Peritoneal Dialysis, Withdrawal of Care, or Other reasons
- Subject has discontinued from the study.

Note: How to assess the above events has been described in **Error! Reference source not found.** the Binary Analysis section.

- All the other subjects will be considered event free and will be censored on visit day (visit day can vary from lower limit to upper limit of visit window).

This endpoint will be evaluated on the mITT population through 1-month, 3-months, 6-months, and 12-months.

## 5.4 Exploratory endpoints

The following endpoint may be evaluated in an exploratory fashion. Data will be collected throughout the course of the investigation in support of this endpoint.

Kit Component Safety and Performance, defined as the overall rate of the catheter's procedure kit component complications from time of procedure to discharge.

Subject will be considered as having a catheter's procedure kit component complication if the following event occurs:

- **Procedure Overview Part 1 CRF Page:** Were there any complications with any of the kit components: Equals Yes

The rate of catheter's procedure kit component complications with 95% confidence interval from the exact binomial method will be presented. All ITT subjects would be considered as evaluable for this endpoint and used in the denominator of rate estimation.

# 6 Summary of General Study Data

## 6.1 Subject Disposition

Subject disposition data is collected on the 'Subject Disposition' and 'Disposition – End of Study' CRF pages.

The summary of the number of subjects enrolled, screen failure, device inserted but subject did not undergo first dialysis session, treated with study device, eligibility met but device not inserted, eligibility met but procedure not initiated, completed the study, and discontinued from the study by reason of discontinuation will be provided. Screen failures will be summarized for each inclusion/exclusion criteria that were not met.

## 6.2 Protocol Deviations

The number of subjects with protocol deviations will be summarized with descriptive statistics by nature of the deviation. The major or minor deviations will be identified and classified as in Appendix 3 prior to data analyses of major reportings.

## 6.3 Demographics and Baseline Variables

Demographics and baseline characteristics will be summarized with descriptive statistics using the ITT population. Summary statistics for categorical variables will include frequency counts and percentages and for continuous variables will include mean, standard deviation, minimum, median, and maximum.

Demographics and baseline characteristics variables include:

- Age at screening (year)
- Sex (Male, Female)
- Race (American Indian or Alaskan Native, Asian, Black or African American, Native Hawaiian or Other Pacific Islander, White, Not Reported, and Unknown)
- Ethnicity (Hispanic or Latino, Not Hispanic or Latino, Not Reported, and Unknown)
- Baseline Weight
- Baseline Height
- Baseline Body mass index (BMI) calculated from weight and height.

Background disease characteristics including medical history and dialysis history will also be summarized.

## **6.4 Follow-up Visit Summary**

Follow-up visit summary and listing will be presented for mITT population.

## **6.5 Index Procedure**

Procedure overview details will be summarized for ITT population.

## **6.6 Hemodialysis Catheter Assessment**

Summary of hemodialysis catheter assessments will be presented for mITT population at 1-, 3-, 6-, 12- months. In the listing, assessments done at unscheduled visits will also be presented.

## **6.7 Most Recent Dialysis Session Blood Flow Rate**

Dialysis session blood flow rates reported in scheduled and unscheduled visits will be presented in a listing for mITT population.

## **6.8 Hemodialysis Catheter Re-Interventions**

Hemodialysis catheter re-interventions will be summarized for mITT population.

## **6.9 Device Deficiencies**

All device deficiencies will be summarized by the failure code.

# **7 Safety Analysis**

Collection of AEs will begin immediately following subject enrollment, during the index procedure through final subject follow-up visit or early termination.

An overall summary including the number and percentage of subjects with at least one AE, total number of AEs, total number of SAEs, total number of UADEs, AEs by relationship to the Device/Index Procedure, and AEs by severity of the event will be summarized for the ITT subjects. In addition, the following summary tables will be provided:

- Number of AEs by System Organ Class (SOC) and Preferred Terms (PT)
- Number of SAEs by System Organ Class (SOC) and Preferred Terms (PT)
- Number of AEs by relationship to Study Device by System Organ Class (SOC) and Preferred Terms (PT)
- Number of AEs by relationship to Procedure by System Organ Class (SOC) and Preferred Terms (PT)
- Number of AEs by severity by System Organ Class (SOC) and Preferred Terms (PT)

Listing of all AEs, SAEs, ADE, and UADEs will be provided.

## 8 Interim Analysis Plan

An interim analysis will be conducted after all eligible patients have completed their 3-months follow-up visit. The Primary endpoint of combined complications will be analyzed and reported. Secondary endpoints will be reported with descriptive statistics.

## 9 SAP Revision History

Version Number	Rationale for Change	Section or Page Affected	Description of Change
1.0	Original SAP		

## 10 Appendix

Appendix 1.1 Tables/Listing/Figures Shell for 3-Month Reporting

Appendix 1.2 Tables/Listing/Figures Shell for Final Reporting

Appendix 2 Derived Data Specification

Appendix 3 Deviations: Major/Minor Classification
